9.1.2 Sensitivity Analysis

The following sensitivity analyses for the primary endpoint will be performed for the ITT population, unless otherwise noted.

1) PP Population

The primary efficacy analysis will be repeated for PP population.

2) Handling of Withdrawal

For classification of patients into success and failure, the primary endpoint will be modified as follows to explore the impact of missing data, withdrawals, or patients who did not undergo an invasive procedure.

- Patients who withdrew from the study before undergoing the primary invasive procedure but whose last observation of platelet count was $\geq 50 \times 10^9/L$ with an increase of $\geq 20 \times 10^9/L$ from baseline will be classified as success, if he/she did not receive platelet transfusion and rescue therapy for bleeding.
- Patients who did not undergo an invasive procedure but whose platelet count was $\geq 50 \times 10^9/L$ with an increase of $\geq 20 \times 10^9/L$ from baseline at least once within 14 days after randomization will be classified as success, if he/she did not receive platelet transfusion and rescue therapy for bleeding.

3) Patients Data Based Analysis

For classification of patients into success and failure, the primary endpoint will be modified as follows based on platelet count at platelet transfusion assessment.

- Patients whose platelet count was $\geq 50 \times 10^9/L$ at platelet transfusion assessment will be considered as success regardless of preoperative platelet transfusion, if he/she (1) underwent invasive procedure, (2) did not receive platelet transfusion within 7 days after the primary invasive procedure, and (3) did not receive rescue therapy for bleeding from the date of randomization through 7 days after the primary invasive procedure. If platelet count at platelet transfusion assessment was missing, the patients will be considered as failure.

9.2 Secondary Endpoints

The following analyses for secondary endpoints will be conducted in the ITT population.

9.2.1 Proportion of Patients Requiring no Platelet Transfusion During the Study

A secondary endpoint is the proportion of patients who required no platelet transfusion during the study. A patient will be considered as success for this endpoint if he/she required no platelet transfusion and received the invasive procedure during the study. All other patients will be considered as failures.

9.2.1.1 Analysis

The number and proportion of patients who required no platelet transfusion during the study will be calculated by treatment group. The proportions will be presented along with 95% CIs. The proportion of patients who required no platelet transfusion during the study in the S-888711 group will be compared with that in the placebo group using the CMH test adjusted by the stratification factors. In addition, the differences in the secondary endpoint and its 95% CI will be calculated.

9.2.2 Proportion of Responders

A responder will be defined as the patient who achieved the following criterion, that is a platelet count of $\geq 50 \times 10^9/\text{L}$ with an increase of $\geq 20 \times 10^9/\text{L}$ from baseline without platelet transfusion at least once during the study. All patients in the ITT population will be classified into either responder or nonresponder for evaluating the proportion of responders during the study. A patient who had platelet transfusion will be considered as a responder if he/she achieved the responder criterion before receiving the first platelet transfusion. However, a patient will be considered as nonresponder if their platelet count met the responder criterion only after platelet transfusion.

In evaluating the proportion of responders at each scheduled time point (Day 5, 6, 7, 8, 10, 12, 14, 17, 21, 28, and 35), a patient will be counted as a responder if all of the following conditions are satisfied:

- Patients achieved a platelet count of $\geq 50 \times 10^9/\text{L}$ with an increase of $\geq 20 \times 10^9/\text{L}$ from baseline at the evaluation point.
- Patients received no platelet transfusion through the evaluation point.

Missing platelet count at each scheduled time point will not be imputed.

9.2.2.1 Analysis

The number and proportion of responders during the study will be calculated by treatment group. The responder rates will be presented along with 95% CIs, which will be calculated with the Clopper-Pearson method. The proportion of responders during the study in the S-888711 group will be compared with that in the placebo group using the CMH test adjusted by the stratification factors. In addition, the differences in the responder rate and its 95% CI will be calculated.

The number and proportion of responders will be calculated by treatment group at each time point. This analysis will be performed for the ITT population with observed values.

9.2.3 Duration of the Increase in Platelet Count

The duration of the increase in platelet count will be defined as the number of days during which the platelet count was maintained as $\geq 50 \times 10^9/\text{L}$, and it will be calculated based on the platelet count at scheduled time points (Days 1, 5, 6, 7, 8, 10, 12, 14, 17, 21, 28, and 35). The detail of the calculation is as follows.

Let (x_i, y_i) be the observed value at scheduled time point i , where $i = 1, 2, \dots, c$ and $c (\leq 12)$ can be different for each patient. For $i > 1$, x_i is the day from initial administration of the study drug to Visit i defined as (the measurement date at Visit i) – (date of initial dose of the study drug) + 1, and y_i is the observed platelet count [$\times 10^9/\text{L}$], respectively. The baseline value represents (x_1, y_1) , where $x_1 = 1$. Let L_i be the line connecting (x_i, y_i) and (x_{i+1}, y_{i+1}) , and $(z_i, 50)$ be the intersection point between L_i and $y = 50$. Then, the duration of the platelet count will be calculated as $D = \sum_i d_i$, where

$$d_i = \begin{cases} x_{i+1} - x_i, & \text{if } y_i \geq 50 \text{ and } y_{i+1} \geq 50 \\ x_{i+1} - z_i, & \text{if } y_i < 50 \text{ and } y_{i+1} \geq 50 \\ z_i - x_i, & \text{if } y_i \geq 50 \text{ and } y_{i+1} < 50 \\ 0, & \text{if } y_i < 50 \text{ and } y_{i+1} < 50 \end{cases}.$$

If there is a missing assessment at Visit $(i+1)$, L_i should be the line connecting (x_i, y_i) and (x_{i+2}, y_{i+2}) , where (x_{i+2}, y_{i+2}) represents the next visit with data available.

9.2.3.1 Analysis

Median and quartiles for the duration of the increase in platelet count will be calculated by treatment group with or without platelet transfusions. The duration in the S-888711 group will be compared with that in the placebo group using van Elteren test stratified with platelet transfusion during the study. In addition, to explore an efficacy of S-888711 compared to platelet transfusion, the duration in the S-888711 group without platelet transfusion will be compared with that in the placebo group with platelet transfusion using Wilcoxon rank sum test.

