2. STUDY OVERVIEW

This is a phase 3, multinational, randomized, double-blind, placebo-controlled study to assess the safety and efficacy of S-888711 for the treatment of thrombocytopenia in patients with CLD undergoing elective invasive procedures. The study consists of 3 periods:

[figure not shown]
- Screening period: up to 28 days prior to randomization
- Treatment period: up to 7 days (Days 1 to 7)
- Post-treatment period: through 28 days post-treatment

The maximum study duration for each patient will be 63 days. Potential patients who provide written informed consent will be screened for eligibility, and eligible patients will be randomized in a 1:1 ratio to either S-888711 3 mg once daily for up to 7 days or matched placebo control. The randomization will be stratified by primary invasive procedure (liver ablation/coagulation or other invasive procedures) and baseline platelet count ($< 35 \times 10^9/L$ or $\geq 35 \times 10^9/L$).

Patients will begin once daily treatment with assigned study medication on Day 1 after randomization and will receive study medication for up to 7 days. A platelet count will be performed on Days 5, 6, and 7 prior to administration of study medication. After the final dose of study medication, patients will continue the protocol-specified assessments and procedures in the Post-treatment period.

The planned invasive procedure will be performed in the Post-treatment period between Days 9 and 14. A platelet count will be performed on or after Day 8, but no more than 2 days prior to the elective invasive procedure in order to assess the need for a platelet transfusion before the planned elective procedure. A preoperative platelet transfusion must be performed if the platelet count is $< 50 \times 10^9/L$.

Study Schematic

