6.2 Statistical Testing

Unless otherwise noted, all statistical tests will be performed at a two-sided significance level of 0.05.

A gatekeeping procedure will be employed for sequentially testing the important secondary endpoints (see [Appendix 2](#)). If the primary endpoint is statistically significant, the secondary endpoints will be tested at the 0.05 level (two-sided) in sequence.

Sequential testing for the secondary endpoints will be conducted in the following order:

- The comparison between S-888711 and placebo in the proportion of patients who require no platelet transfusion during the study
- The comparison between S-888711 and placebo in the proportion of responders: patients who achieve a platelet count of $\geq 50 \times 10^9/\text{L}$, with an increase of $\geq 20 \times 10^9/\text{L}$ from baseline at any time during the study
- The comparison between S-888711 and placebo in the duration of platelet count $\geq 50 \times 10^9/\text{L}$
- The comparison between S-888711 without platelet transfusion and placebo with platelet transfusion in the duration of platelet count $\geq 50 \times 10^9/\text{L}$

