9.1.1 Primary Analysis

The number and proportion of patients who required no platelet transfusion prior to the primary invasive procedure and no rescue therapy for bleeding from the date of randomization through 7 days after the primary elective procedure will be calculated by treatment group. The primary endpoint will be presented along with 95% confidence intervals (CIs), which will be calculated with the Clopper-Pearson method.

The proportion of patients who required no platelet transfusion in the S-888711 group will be compared with that in the placebo group using the Cochran-Mantel-Haenszel (CMH) test adjusted by the stratification factors, i.e., the four strata:

- Platelet count at randomization $< 35 \times 10^9/\text{L}$ and liver ablation/coagulation
- Platelet count at randomization $< 35 \times 10^9/\text{L}$ and other invasive procedure
- Platelet count at randomization $\geq 35 \times 10^9/\text{L}$ and liver ablation/coagulation
- Platelet count at randomization $\geq 35 \times 10^9/\text{L}$ and other invasive procedure.

In addition, the differences in the primary endpoint and its 95% CI using Wald method (see [Appendix 3](#)) will be calculated.

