13. CHANGES FROM PROTOCOL

- An analysis using the van Elteren is added in order to compare the duration of the increase in platelet count between S-888711 and placebo group for the ITT population (see [Section 9.2.3](#))
- Summary of significant TEAEs is removed because this event was not defined in the protocol.

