Appendix 2 Testing Procedure for Primary and Important Secondary Endpoints

S-888711 for up to 7 days vs. Placebo

Testing the Primary Efficacy Endpoint:

The null hypothesis is that there is no difference between S-888711 for up to 7 days and placebo groups regarding the proportion of patients, who require no platelet transfusion prior to the primary invasive procedure and no rescue therapy for bleeding from randomization until 7 days after the primary elective procedure.

↓ if rejected^a

Testing the Secondary Efficacy Endpoint 1:

The null hypothesis is that there is no difference between S-888711 for up to 7 days and placebo groups regarding the proportion of patients who require no platelet transfusion during the study.

↓ if rejected^a

Testing the Secondary Efficacy Endpoint 2:

The null hypothesis is that there is no difference between S-888711 for up to 7 days and placebo groups regarding the proportion of patients who achieve a platelet count of $\geq 50 \times 10^9/L$ with an increase of $\geq 20 \times 10^9/L$ from baseline at any time during the study.

↓ if rejected^a

Testing the Secondary Efficacy Endpoint 3:

The null hypothesis is that there is no difference between S-888711 and placebo groups regarding the duration of the platelet count $\geq 50 \times 10^9/L$.

↓ if rejected^a

Testing the Secondary Efficacy Endpoint 4:

The null hypothesis is that there is no difference between S-888711 for up to 7 days without platelet transfusion and placebo with platelet transfusion groups regarding the duration of the platelet count $\geq 50 \times 10^9/L$.

[a] If superiority of S-888711 to placebo is demonstrated at the two-sided significance level of 0.05, then the next hypothesis will be tested.

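### The gatekept test of platelet-count duration is stratified by transfusion during the study, a post-randomisation result of treatment, so it does not test the whole-group null in SAP Appendix 2

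*SAP*

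**What the plan says.** - **Test.** SAP 9.2.3.1: duration in the S-888711 group is "compared with that in the placebo group using van Elteren test stratified with platelet transfusion during the study".
- **Hypothesis.** SAP Appendix 2, secondary endpoint 3, gives the null as "there is no difference between S-888711 and placebo groups regarding the duration of the platelet count" at or above 50 × 10⁹/L. SAP 13 describes the added van Elteren analysis as comparing "the duration of the increase in platelet count between S-888711 and placebo group for the ITT population".
- **Gate.** SAP 6.2: "If the primary endpoint is statistically significant, the secondary endpoints will be tested at the 0.05 level (two-sided) in sequence". Duration is third among the secondaries. First is the proportion without transfusion, defined in SAP 9.2.1: "A patient will be considered as success for this endpoint if he/she required no platelet transfusion and received the invasive procedure during the study".
- **Stratum variable.** SAP 2: "A preoperative platelet transfusion must be performed if the platelet count is" below 50 × 10⁹/L. That count is taken on or after Day 8.
- **Endpoint.** SAP 9.2.3 defines duration as days at or above 50, and "it will be calculated based on the platelet count at scheduled time points". It has no rule for counts after a transfusion, whereas the responder definition in SAP 9.2.2 gives no credit for them.
- **Other tests.** The primary analysis is done "using the Cochran-Mantel-Haenszel (CMH) test adjusted by the stratification factors, i.e., the four strata", which are baseline platelet count and procedure type. The two secondary tests before duration are adjusted by the same factors.
- **Protocol.** Section 8.10.1.2.3 first describes medians and quartiles by arm with or without transfusion, then names a Wilcoxon rank sum test between the two groups.

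**The concern.** A stratified rank test compares an S-888711 patient only with placebo patients in the same stratum. Here the stratum is decided after randomisation, by a count of the same kind and at the same threshold as the endpoint. If the drug spares patients a transfusion, the untransfused S-888711 patients and the untransfused placebo patients are differently selected, and so are the transfused ones. Randomisation does not protect either comparison.

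The position in the sequence sharpens this. Test 3 is reached only after the arms have been shown to differ on secondary endpoint 1, which is closely tied to the stratum variable. Test 4 compares untransfused S-888711 patients with transfused placebo patients, again subsets formed after randomisation. No comparison of the randomised groups on duration is left. At stake are the meaning of the duration claim and access to test 4, which is blocked if test 3 fails.

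**Working it through.** **1. The plan's own figures.** SAP 4.3 gives no power for duration. For the primary endpoint (20% versus 70%, 100 per arm) the null SE is √(2 × 0.45 × 0.55/100) = 0.0704 and the alternative SE is √((0.7 × 0.3 + 0.2 × 0.8)/100) = 0.0608. So (0.50 − 1.96 × 0.0704)/0.0608 ≈ 5.95, and power exceeds 99.99%, consistent with the stated 99%. Below, 70% and 20% stand in for the transfusion-free rates. This is an approximation, because they are planning rates for a composite endpoint.

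**2. What the stratified test compares.** Expected strata are 70 versus 20 untransfused and 30 versus 80 transfused.
- Drug–placebo pairs compared: 70 × 20 + 30 × 80 = 3,800 of 100 × 100 = 10,000 (38%).
- Pairs never compared: 70 × 80 = 5,600 (untransfused drug, transfused placebo) and 30 × 20 = 600.
- At the Japanese phase 3 pre-procedure rates (38/48 and 6/48): 38 × 6 + 10 × 42 = 648 of 48 × 48 = 2,304 (28%).

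These counts describe the comparison; they do not measure power.

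**3. Simulation.** 100 per arm, two-sided 0.05. The van Elteren statistic is Σ wₖ[Rₖ − n₁ₖ(Nₖ+1)/2] with wₖ = 1/(Nₖ+1), divided by its tie-corrected standard error. All duration distributions are assumed.

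*Level kept.* With the same joint distribution of duration and transfusion in both arms, the SAP test rejects in about 5%. It also does so at 70/20 if duration is unrelated to transfusion.

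*Error towards placebo.* Whole-group durations are identical. A latent variable with correlation ρ to duration decides transfusion, with arm-specific cut-offs giving 70/20.

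| ρ | SAP test, towards placebo | Wilcoxon, two-sided |
|---|---|---|
| 0.3 | about 35% | about 5% |
| 0.5 | about 76% | about 5% |
| 0.8 | about 100% | about 5% |

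*Lost power.* Transfused patients have durations 1 SD shorter, and the drug acts only by avoiding transfusion. Wilcoxon rejects in 90%; the SAP test rejects in 5%, both directions together.

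*Error towards S-888711.* Transfusion lengthens duration by δ and the drug adds 0.5δ in each stratum. Whole-group means are then equal: 0.3δ + 0.5δ = 0.8δ. The SAP test favours S-888711 in 32% (δ = 0.5 SD) and 84% (δ = 1 SD); Wilcoxon rejects in about 5%.

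*Opposite ordering of power.* Untransfused means are 12.39 versus 0.74 days (Protocol 1.3, Japanese phase 3, for the stricter responder criterion) and the transfused mean is 12 days in both arms. At 70/20, Wilcoxon has 66% or 76% power, depending on the assumed spread, against 99% for the SAP test. At 79.2/12.5 it has 30% or 47%, against 92% to 93%. With transfused means of 1 to 5 days instead, the SAP test has 87–99% (70/20) or 69–93% (79.2/12.5), and Wilcoxon is not lower.

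**The case against.** The best defence is that stratifying separates the drug's effect from that of the transfusion. SAP 9.2.3 counts days at or above 50 even when a transfusion produced them, and placebo patients are expected to receive most transfusions. A pooled test would credit those days to placebo. SAP 9.2.2 and test 4 show the same wish to keep the two effects apart. This part stands: the choice is partly one of estimand, and a pooled test without a stated rule for post-transfusion days would leave the question open. It does not rescue the strata, because conditioning on a result of treatment does not remove the transfusion's effect. The SAP also gives no reason for them and states a whole-group hypothesis.

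The analysis was pre-specified and disclosed in SAP 13. That is a fair point on process, but it does not make the test match its null.

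A reader might infer that the SAP overrode a pooled Wilcoxon test fixed in the protocol. Protocol 8.10.1.2.3 does not settle that: a pooled test is a natural reading, but the sentence follows a split by transfusion status. A reader might also infer that the unstratified test is always the more powerful; the last case above shows that it is not. Nor is the stratum variable identical to secondary endpoint 1, which also requires that the procedure took place.

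**Conclusion.** The mismatch between test and hypothesis is plain from the text and needs no assumed number. Test 3 answers a question within transfusion groups, while Appendix 2 and Section 13 read it as a difference between the randomised groups. It keeps its level if duration and transfusion have the same joint distribution in both arms, or if duration is unrelated to transfusion. The first is hard to maintain once endpoint 1 has been rejected; the second is unlikely when both turn on a count of 50.

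It would go too far to say that test 3 will fail, or that it will give a false win. The documents give no distribution of duration by transfusion status, so the percentages above are illustrations. Equal whole-group durations alongside a 50-point difference in transfusion is a device for checking level, and rejection towards placebo is not what the Japanese data suggest. Footnote a of Appendix 2 requires superiority of S-888711 before the next test, so such a rejection would close the gate to test 4. Confidence is high on the mismatch and low on its size and direction in this trial. The primary endpoint and secondary tests 1 and 2 are unaffected.

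**What to change.** In SAP 9.2.3.1, make gatekept test 3 a comparison of the randomised groups in the ITT population. Use either an unstratified Wilcoxon rank sum test or a van Elteren test on the four randomisation strata of SAP 9.1.1.

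State with that test how days at or above 50 after a transfusion count. Either count them as observed under SAP 9.2.3, with a sensitivity analysis that gives no credit after the first transfusion (in line with SAP 9.2.2), or make the no-credit rule primary and the observed count the sensitivity analysis.

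Keep the transfusion-stratified van Elteren test as supportive, outside the gate.

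The cost is one change of SAP wording, one program change and one extra derivation, with no new data. The statistical price is a possible loss of power if transfused patients turn out to have long durations.

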9.2.4 Proportion of Patients who Required Rescue Therapy

The number and proportion of patients who received rescue therapy for bleeding events during the study will be calculated for each treatment group. Platelet preparations, other blood preparations including red blood cells and plasma, and volume expanders will be considered as rescue therapy for bleeding events.

The number and proportion of patients who received antithrombotic drugs for thrombotic events during the study will be summarized similarly.

9.2.5 Frequency of Platelet Transfusion and Dose (Unit) Transfused During the Study

The number and proportion of patients who received platelet transfusion during the study will be calculated for each treatment group, and the reasons for platelet transfusion will be summarized. For the patients who received at least one platelet transfusion, the number of platelet transfusions during the study will be summarized by treatment group.

Average dose (unit/bags) of platelet transfusion will be calculated for each patient and then summarized by treatment group if appropriate. If the total amount of transfused platelets is able to be estimated for patients, it will be performed with reference to a minimum contents based on a guidance on platelet preparations in each country taking into account the method for collection (apheresis/pooled).

9.2.6 Time Course of Platelet Count

Unless otherwise specified, the following analyses will be performed for patients who received and who didn't receive platelet transfusions.

Summary statistics for platelet count will be calculated at each scheduled time point (Days 1, 5, 6, 7, 8, 10, 12, 14, 17, 21, 28, and 35) by treatment group. Summary statistics for the change in platelet count from baseline will also be calculated.

The time course of the median, 25% and 75% quartile of platelet count will be graphically displayed by treatment group. Reference line which shows $y = 50 \times 10^9/\text{L}$ will be drawn in the figure. In addition, the time course of the mean and standard deviation of platelet count change from baseline will be graphically displayed by treatment group. Reference line which shows $y = 20 \times 10^9/\text{L}$ will be drawn in the figure.

Summary statistics for the maximum platelet count and the maximum change in platelet count of each patient will be calculated by treatment group. Baseline value will not be included in this analysis.

For the patients who received no platelet transfusion, the time point at which each patient showed the maximum platelet count will be summarized by treatment group. If maximum platelet count for the patient is observed at more than one time point, the earliest time point will be used in this analysis.

